6.2.6 Day 63 (\pm 2 days) Follow-Up (phone)

• Query for adverse events (phone call only for subjects not entering the active treatment extension)

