SPH3127 or placebo for 8 weeks in patients with mild-to-moderate

ulcerative colitis.

To investigate the pharmacokinetics and pharmacodynamics of daily oral administration of SPH3127 or placebo for 8 weeks in patients with mild-

to-moderate ulcerative colitis.

Study Design: The SPH3127-US-01 is a multi-center, randomized, double-blind, placebo-controlled study to evaluate the safety and preliminary efficacy of SPH3127 for the treatment of mild-to-moderate ulcerative colitis.

The study consists of five (5) visits: a Screening/confirmation of diagnosis visit, a study initiation visit (Day 1) and 2 subsequent treatment and assessment visits at 4-week intervals (Day 28; 56) and a single-day treatment and safety visit after the first 2 weeks of treatment (Day 14). All randomized subjects will have the opportunity to enter an active treatment

extension. The study blind (dose SPH3127) will be maintained through the extension period. Medication will be dispensed at 8-week intervals in eight 2-week blister packs for an additional 10 months in the active treatment extension. Safety information (adverse events) will be collected over this period. In addition, clinical laboratory tests and vital signs will be collected at 2-month intervals. Rectal bleeding and stool frequency will be collected daily using a subject diary. Flexible sigmoidoscopy will be performed at the final site visit (Day 336). The study design is presented in the STUDY SCHEMATIC (Figure 1).

The duration of subject participation in the primary study is approximately 13 weeks, including Screening and a follow-up call 1 week after the last dose (for those subjects who choose not to enter the extension). Subjects participating in the optional active treatment extension will participate for an additional 10 months.

Study Endpoints:

In this exploratory study, a variety of safety endpoints will be evaluated, including, but not limited to:

- 1. Vital signs (systolic and diastolic blood pressure (seated), temperature and pulse/heart rate);
- 2. Physical examination;
- 3. Clinical laboratory tests (hematology, serum chemistry, urinalysis); and,
- 4. Adverse events.

In this exploratory study, a variety of efficacy and translational endpoints will be evaluated, including, but not limited to:

- 1. Proportion of patients in clinical remission at week 8;
- 2. Endoscopic improvement (MCES ≤ 1) at week 8;
- 3. Endoscopic remission (MCES subscore of 0) at week 8;

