After the 12-week trial period (including screening), all randomized subjects will have the opportunity to enter an optional active treatment extension for an additional 10 months. Those subjects receiving Treatment A and who choose to enter the extension will continue on Treatment A in a blinded manner (will not know SPH3127 dose). Those subjects receiving Treatment B and who choose to enter the extension will continue on Treatment B in a blinded manner (will not know SPH3127 dose). Those subjects receiving Treatment C (placebo) and who choose to enter the extension will be randomized to receive Treatment A or Treatment B in a blinded manner (will not know SPH3127 dose). Those subjects who choose not to enter the optional active treatment extension will receive a follow-up safety call one week after the last treatment (D63). The STUDY SCHEMATIC is presented in Figure 1.

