- Plasma biomarkers (1', 2', 4', 8').

6.2.5 *Visit Day* 56 (\pm 2 days)

The following procedures will be performed on **Day 56 (pre-dose)**:

- Physical examination
- ECG;
- Clinical laboratory assessments;
- Concomitant medications;
- Adverse events;
- Vital signs assessment (systolic and diastolic blood pressure (seated), heart rate, temperature (-10" pre-dose);
- PK (-10" pre-dose);
- Plasma biomarkers (-10" pre-dose);
- Fecal calprotectin (stool collection);
- Take morning oral dose on-site and drug accountability.

The following procedures will be performed on **Day 56 (post-dose)**:

- Vital signs assessment (systolic and diastolic blood pressure (seated), temperature (30", 2', 4', 8');
- PK (15", 30", 1', 2', 4', 8');
- Plasma biomarkers (1', 2', 4', 8')
- Dispense medication (for those participating in the active extension).
- Modified Mayo Clinical Score
 - Stool frequency (from diary)
 - Rectal bleeding (from diary)
 - Flexible sigmoidoscopy within 2 days of visit to allow for bowel prep/cleansing)
- UC lesion tissue collection (during sigmoidoscopy) for Robarts Histology Index (RHI) and biomarkers (within 2 days of visit).

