6.2.7 Active Treatment Extension

All randomized subjects will have the opportunity to enter an active treatment extension after the last main study visit (Day 56). A phone call will be made to each subject to confirm interest in participating on Day 46 ± 2 . Medication will be dispensed at 8-week intervals in the same 2-week blister packs as the main study for an additional 10 months in the active treatment extension. Those subjects receiving Treatment A (50 mg SPH3127 total daily dose) and who choose to enter the extension will continue on Treatment A in a blinded manner (will not know SPH3127 dose). Those subjects receiving Treatment B (100 mg SPH3127 total daily dose) and who choose to enter the extension will continue on Treatment B in a blinded manner (will not know SPH3127 dose). Those subjects receiving Treatment C (placebo) and who choose to enter the extension will be randomized to receive Treatment A or Treatment B in a blinded manner (will not know SPH3127 dose). Safety information (i.e., adverse events, clinical laboratory tests, vital signs, concomitant medications) will be collected at the designated intervals (every 8weeks) in the Schedule of Assessments. Rectal bleeding and stool frequency will be collected daily using a subject diary. At the final site visit (D336), a physical examination and flexible sigmoidoscopy (within 2 days of visit) will also be performed.

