9.1 Documenting Adverse Events

The recording of AEs (regardless of their relationship to study drug) will begin with the Screening Visit until the Final Visit (Day 56) or Early Termination Visit. If the Investigator is made aware of an AE up to 7 days after the last dose of study drug the AE will be followed to resolution. For those patients who enter the optional active treatment extension, Investigator(s) will query patients for AEs when they visit the site to pick up their medication every 8 weeks. Investigator(s) will monitor each patient closely for AEs. At each visit, the Investigator will document all observed or volunteered AEs.

The Investigator(s) should always attempt to group signs and symptoms into a single term that constitutes a single unifying diagnosis. Adverse Events will be classified using the latest version of the Medical Dictionary for Regulatory Activities (MedDRA) classification system. AEs reported from the first dose of IP until 7 days after the last dose of IP will be considered as treatment-emergent AEs (TEAEs) and will be summarized descriptively. The Investigator's opinion of the association of each AE to study drug, the duration (date of onset / date of resolution), frequency, intensity, countermeasures (treatment), and the outcome of each AE will be documented. Each adverse event must be recorded separately. Multiple occurrences of a single PT in a patient will only be counted once at the maximum severity/grade. All AEs will be summarized by relatedness to IP. Any AEs leading to death or discontinuation of IP will also be summarized.

Any medical condition or laboratory abnormality that is present at subject screening and prior to the first dose of study drug should be considered as baseline, recorded in medical history, and should not be reported as an AE. However, if the medical condition worsens at any time during the study after the first dose of study drug it should be recorded as an adverse event.

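### Placebo patients who start SPH3127 in the extension have no scheduled adverse-event query on drug until Day 112, because the Day 63 call goes only to non-entrants

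*Combined protocol and SAP*

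**What the plan says.** **The switch to drug.** For Treatment C, section 6.2.7 reads "placebo) and who choose to enter the extension will be randomized to receive Treatment A or Treatment B". Section 6.2.5 puts the Day 56 AE query, laboratory tests and ECG before the on-site morning dose. It then lists, among the post-dose procedures, "Dispense medication (for those participating in the active extension".

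**The Day 63 call.** Section 6.2.6 reads "Query for adverse events (phone call only for subjects not entering the active treatment extension". Section 4.1 says "Those subjects who choose not to enter the optional active treatment extension will receive a follow-up safety call one week after the last treatment". The Study Summary describes "a follow-up call 1 week after the last dose (for those subjects who choose not to enter the extension", and Schedule footnote d agrees.

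**Extension follow-up.** Section 6.2.7 says "Safety information (i.e., adverse events, clinical laboratory tests, vital signs, concomitant medications) will be collected at the designated intervals (every 8weeks". Section 9.1 says "Investigator(s) will query patients for AEs when they visit the site to pick up their medication every 8 weeks". The first such visit in the Schedule is Day 112 ± 4.

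**First exposure in the main study.** Section 6.2.2 has the first dose taken on site, with vital signs up to 8 hours afterwards. Section 6.2.3 then sets a Day 14 visit whose main purpose is safety and compliance, with an AE query.

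**The concern.** A former placebo patient's first SPH3127 tablet is a first exposure, like that of a Treatment A or B patient on Day 1. The plan follows the two differently and gives no reason. Everything collected at Day 56 for such a patient, including the vital signs after the morning dose, describes placebo. Nothing is then scheduled to ask about AEs for about 8 weeks.

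What is at stake is the quality of AE data in newly exposed patients. Section 9.1 requires that "the duration (date of onset / date of resolution), frequency, intensity, countermeasures (treatment), and the outcome of each AE will be documented". For a symptom the patient does not volunteer, these details would rest on up to about 8 weeks of recall.

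Section 1.3.1 gives some reason to care about early events. Seven days of 100 to 400 mg/day produced mild, reversible hypotension, neutropenia and ALT increases (onset days not given). Liver-test elevations were more frequent than on placebo, without apparent relation to dose.

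**Working it through.** **Inputs.** Schedule: Day 56 ± 2, Day 112 ± 4, Day 14 ± 2 and Day 63 ± 4. Section 6.2.6: Day 63 ± 2. Section 4.1: 10 patients per arm, 30 in all. The documents give no extension entry rate, so 50%, 70% and 100%, equal across arms, are assumed. The first extension tablet is assumed to be taken on the day of the Day 56 visit. If the first active tablet is taken the next morning, each interval from the switch is one day shorter.

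**1. The plan's own interval.** 8 weeks × 7 = 56 days. Days 56, 112, 168, 224, 280 and 336 are each 56 days apart, so the Schedule matches the text.

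**2. Wait from switch to first scheduled AE query, as written.**
- Nominal: 112 − 56 = 56 days
- Shortest: (112 − 4) − (56 + 2) = 108 − 58 = 50 days
- Longest: (112 + 4) − (56 − 2) = 116 − 54 = 62 days

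**3. The same wait after first exposure in the main study.**
- Nominal: 14 − 1 = 13 days
- Range: 12 − 1 = 11 to 16 − 1 = 15 days

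Scheduled AE queries in the first 8 weeks on drug number 3 in the main study (Days 14, 28 and 56) and 1 for a former placebo patient (Day 112).

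**4. Wait if the Day 63 call includes entrants.**
- Nominal: 63 − 56 = 7 days
- ± 2 window: 61 − 58 = 3 to 65 − 54 = 11 days
- ± 4 window: 59 − 58 = 1 to 67 − 54 = 13 days

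Queries in the first 8 weeks on drug rise from 1 to 2.

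**5. What remains after the call.**
- Nominal: 112 − 63 = 49 days
- ± 2 window: 108 − 65 = 43 to 116 − 61 = 55 days
- ± 4 window: 108 − 67 = 41 to 116 − 59 = 57 days

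The call shortens the time to the first query a great deal. It shortens the longest stretch without a query only from 56 to 49 days.

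**6. Patients and calls.**

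| Assumed entry | Extra calls (of 30) | To newly exposed (of 10) | To patients already on drug |
|---|---|---|---|
| 50% | 15 | 5 | 15 − 5 = 10 |
| 70% | 21 | 7 | 21 − 7 = 14 |
| 100% | 30 | 10 | 30 − 10 = 20 |

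**The case against.** The strongest reply is that the Day 63 call is a follow-up after the last dose. Section 10.3 monitors safety through Day 63 for the main study, or through the extension where that applies, so omitting patients who keep dosing fits its purpose. That explains the wording. It does not supply early follow-up for patients whose exposure begins in the extension.

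The remaining counter-arguments limit the size of the point, and they stand:

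- **Other oversight continues.** Section 9.1 asks investigators to monitor closely and to document observed or volunteered AEs, and 9.8 requires SAE reports within 24 hours. A daily diary records bleeding and stool frequency. The sigmoidoscopy falls within 2 days after Day 56 (Schedule footnote b) and may follow the first active tablet. None of these is a scheduled AE query, but they are real contacts.
- **The known risk is low at these doses.** Section 1.3.1 reports that 50 to 200 mg daily for 8 weeks was well tolerated in hypertensive patients, with no dose-limiting toxicity in any study. Dizziness after single doses occurred only at the higher doses. The trial doses were chosen to minimize blood pressure effects. Treatment A is below the 100 to 400 mg/day range, and Treatment B meets its lower end only as a daily total, split into two doses.
- **A call is a blunt tool.** Most of the cited signals are laboratory or blood pressure findings that a phone query will miss unless they cause symptoms. AEs starting after the first week still face about 7 weeks of recall.

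**Conclusion.** The gap is real, and the summary, 4.1, 6.2.6, 6.2.7, 9.1 and the Schedule all agree on it. Up to 10 newly exposed patients wait 56 days (50 to 62) for a first scheduled AE query, against 13 days (11 to 15) in the main study. The figure rests on the first-tablet assumption above and counts scheduled queries only. The point is modest, but worth acting on because the remedy is cheap.

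A reader might infer more, and the documents do not support it:

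- **That these patients are unmonitored for 8 weeks.** Unscheduled reporting and the contacts above remain.
- **That the call restriction delays vital signs and laboratory tests.** These wait until Day 112 because of the 8-weekly extension schedule, and would still do so with the call.
- **That the primary safety objective suffers.** It covers the first 8 weeks, before the switch.
- **That the call would cure the recall problem.** It helps with events in the first week and little after that.

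**What to change.** Make the Day 63 AE call to every patient, including all extension entrants whatever their prior arm. Calling only former placebo patients would disclose their main-study assignment. State one window; ± 2 days is suggested, since 6.2.6 now gives ± 2 and the Schedule ± 4.

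Amend these together, so that no new conflict arises:

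- the Study Summary line, section 4.1, section 6.2.6 and Schedule footnote d, which restrict the call;
- the Schedule's post-study follow-up row label, which would be wrong for patients still dosing;
- sections 6.2.7 and 9.1, which tie extension AE collection to the 8-weekly visits.

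The cost is at most 30 extra phone calls. Up to 20 of them go to patients who have already had 8 weeks of SPH3127, which is the price of keeping the blind. The change also needs a protocol amendment with IRB approval before use (section 14) and any consent revision that follows. It adds no visit, test or blood draw.

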6.2.7 Active Treatment Extension

All randomized subjects will have the opportunity to enter an active treatment extension after the last main study visit (Day 56). A phone call will be made to each subject to confirm interest in participating on Day 46 ± 2 . Medication will be dispensed at 8-week intervals in the same 2-week blister packs as the main study for an additional 10 months in the active treatment extension. Those subjects receiving Treatment A (50 mg SPH3127 total daily dose) and who choose to enter the extension will continue on Treatment A in a blinded manner (will not know SPH3127 dose). Those subjects receiving Treatment B (100 mg SPH3127 total daily dose) and who choose to enter the extension will continue on Treatment B in a blinded manner (will not know SPH3127 dose). Those subjects receiving Treatment C (placebo) and who choose to enter the extension will be randomized to receive Treatment A or Treatment B in a blinded manner (will not know SPH3127 dose). Safety information (i.e., adverse events, clinical laboratory tests, vital signs, concomitant medications) will be collected at the designated intervals (every 8weeks) in the Schedule of Assessments. Rectal bleeding and stool frequency will be collected daily using a subject diary. At the final site visit (D336), a physical examination and flexible sigmoidoscopy (within 2 days of visit) will also be performed.

6.3 Premature Discontinuation

An enrolled subject is defined as having signed an informed consent, met all inclusion/exclusion criteria, been randomized to treatment and having received at least one dose of study drug.

A subject has the right to withdraw from the study at any time for any reason without prejudice or without jeopardizing their medical care. The Investigator must withdraw the subject from the study if the subject requests to be withdrawn.

The Investigator may discontinue a subject from the study when, in his/her judgment it is necessary for any reason, including any of the following:

- Adverse event (serious or non-serious);
- Failure to comply with the protocol;
- Requires a medication that is specifically prohibited by the protocol; or,
- It is in the subject's best interest.

The Investigator may also withdraw a subject upon the request of the Sponsor, or if the Sponsor terminates the study for clinical or administrative reasons.

If a subject is withdrawn from participation in the study, the reason(s) for discontinuation shall be documented. A subject who discontinues the study early (regardless of cause) will be requested to return to the clinic and have all the early termination assessments

performed. If a subject is discontinued from study due to an adverse event, the subject will be followed until the event is resolved or deemed clinically stable.

A subject that has been met all the eligibility criteria at Screening, but not at baseline (Day 1), will be replaced. A subject that has enrolled in the study (signed informed consent, met all inclusion/exclusion criteria, has been randomized and received at least one dose of study drug) that discontinues from the study (for any reason) will not be replaced.

7 DESCRIPTION OF STUDY PROCEDURES

Patients will be assigned a unique study subject identification number at the Screening Visit. Once this number has been assigned to a study subject, it cannot be reassigned.

7.1 Informed Consent

Written informed consent will be obtained for each patient prior to any screening or study-related procedures being performed. The Investigator or trained designee must explain to each patient the nature of the treatment, its purpose, procedures, expected duration and the potential risks and benefits associated with the clinical research study. Each patient will be given the opportunity to discuss questions related to study participation with the Investigator or trained designee and/or with friends and relatives, prior to signing the informed consent form (ICF). Each patient will also be provided with a printed copy of the study ICF detailing the relevant study information. The original ICF will be kept in the Investigator Site File. A notation that written informed consent has been obtained will be made in the subject's medical record.

7.2 Medical History/Demographics

Demographic information and a complete medical history, including any clinically significant pre-existing conditions, concomitant medications and drug allergies, will be collected and recorded at Screening.

7.3 Physical Examinations

Physical examinations will include the examination of the following organ systems - dermatological, head, eyes, ears, nose, mouth/throat/neck, thyroid, lymph nodes, cardiovascular, respiratory, gastrointestinal and neurological.

Physical examinations will be performed at Screening, Days 1, 14, 28 and at the End-of-Study Visit (Day 56; or the Early Termination Visit). In addition, a physical examination will be conducted at the end of the active treatment extension period (Day 336) for those that participate in this portion of the trial. During the physical examination at the End-of-Study Visit (or Early Termination Visit), the subject will be queried regarding any changes in health status since the previous examination.

7.4 ECG

A conventional 12-lead ECG with leads placed on the patient's limbs and on the surface of the chest will be collected at Screening and on Days 1 and 56.

7.5 Stool Sample Collection/Fecal Calprotectin

Stool samples will be collected and split for enteric pathogens such as *Clostridium difficile* and for fecal calprotectin, a marker of UC treatment activity, within 2 weeks after Informed Consent and for fecal calprotectin at Day 28 and Day 56.

7.6 Clinical Laboratory Tests

Viral/bacterial infection (hepatitis B, hepatitis C, HIV, COVID-19, TB) tests will be performed at Screening.

The following clinical laboratory assessments will be performed at the Screening, Day 1, Day 14, Day 28 and Day 56 Visits (or Early Termination Visit), as well as the visits every 2 months during the active treatment extension.

Hematology: white blood cell counts with differential, hemoglobin, hematocrit, platelet count, ESR (screening) and red blood cell count.

Serum chemistry: albumin, total protein, alkaline phosphatase, alanine aminotransferase, aspartate aminotransferase, γ-glutamyltransferase, total bilirubin, blood urea nitrogen, calcium, bicarbonate, chloride, creatinine, glucose, and sodium, potassium, T3, T4, TSH, cholesterol and triglycerides.

Urinalysis: Specific Gravity, pH, protein, glucose, ketone, bilirubin, urobilinogen, blood, nitrite, and leukocytes.

Venous blood samples will be collected and prepared using standard procedures and sent to a certified central laboratory for processing and reporting. Details for collection, handling, processing and shipping of specimens are described in a Study Laboratory Manual (provided separately).

7.7 Urine drug screen, alcohol breathalyzer

A standard urine drug panel screen and alcohol breathalyzer will be administered at Screening.

7.8 Urine pregnancy test/Contraception

Female patients who are pre-menopausal or who have not been surgically sterilized will take a urine pregnancy test at Screening and on Day 1. Female patients who have a negative pregnancy test at Screening and Day 1 and who agree to use adequate birth control methods throughout the entire study (and extension, if applicable) will be enrolled.

Highly effective methods of contraception (i.e., pregnancy rate of less than 1% per year) are: a stable regimen of combined estrogen and progesterone hormonal contraception with inhibition of ovulation, progestogen-only hormonal contraception associated with inhibition of ovulation, intrauterine device, intrauterine hormone releasing system, bilateral tubal occlusion or have a vasectomized partner. Agreement to continuous abstinence is also acceptable.

Non-vasectomized male patients who are sexually active with female partners of childbearing potential must agree to the use condoms during every penile-vaginal intercourse and not donate semen during the trial or within 90 days after the last

investigational product administration. In addition, the female partner of childbearing potential must use a highly effective method of contraception (see above). Non-vasectomized male patients may also agree to continuous abstinence from heterosexual sexual contact.

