7.17 SPH3127 Pharmacokinetics

Blood samples (3 mL/time point) will be collected once at each time point (-10" predose, 15", 30", 1', 2', 4', 8') for PK analysis into anticoagulant tubes containing EDTA-K₂ and centrifuged for 15 min. The pretreated PK plasma samples will be frozen and sent for determination of SPH3127 levels. Sample collection will occur over 8 hours at the study site on Days 1, 28 and 56.

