9.4 Pregnancy

Pregnancy is neither an AE nor an SAE. However, all pregnancies occurring in subjects or their partner will be followed to assess for pregnancy-associated AEs or SAEs such as congenital anomaly. If, at any time between the first study drug dispensing and 7 days after the last dose of study drug, a pregnancy is suspected, the patient/partner will be instructed/requested to return to the study center within 48 hours and undergo a serum

pregnancy test, as confirmation of pregnancy. All confirmed pregnancies must be immediately reported using the appropriate form.

Upon confirmation of a subject pregnancy, no further investigational treatment will be administered. All pregnancies with study drug exposure will be followed until resolution (i.e., termination [voluntary or spontaneous] or birth).

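### Women on placebo who enter the extension are dispensed their first SPH3127 at Day 56 on a pregnancy test about 55 days old, with no retest before exposure

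*Combined protocol and SAP*

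**What the plan says.** Section 7.8 provides that women who are pre-menopausal or not surgically sterilized "will take a urine pregnancy test at Screening and on Day 1", and it makes enrolment conditional on both results being negative. The Schedule of Assessments (4.2) marks the test at those two visits and nowhere else. Section 6.2.2 lists the Day 1 test among the pre-dose procedures.

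The Day 56 lists in 6.2.5 contain no pregnancy test. They do contain, under post-dose procedures, "Dispense medication (for those participating in the active extension". Section 6.2.7 adds: "Those subjects receiving Treatment C (placebo) and who choose to enter the extension will be randomized to receive Treatment A or Treatment B". For these women, the extension is the first exposure to SPH3127.

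During the extension, 6.2.7 states "Safety information (i.e., adverse events, clinical laboratory tests, vital signs, concomitant medications) will be collected at the designated intervals". The laboratory panels in 7.6 (hematology, chemistry, urinalysis) include no pregnancy test.

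Two other controls exist. Sections 5.3 and 7.8 require contraception through the main study and the extension. Section 9.4 provides a serum test that begins with a condition: "If, at any time between the first study drug dispensing and 7 days after the last dose of study drug, a pregnancy is suspected". On a positive result, "Upon confirmation of a subject pregnancy, no further investigational treatment will be administered".

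**The concern.** The plan does not rely on the Screening test for first dosing. It tests again on Day 1, before drug is given, although contraception has already been agreed. Women on placebo meet SPH3127 for the first time in the extension, and there the plan gives no such check, although their last test is about twice as old as the Screening test is on Day 1. The documents give no reason for the difference.

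An early pregnancy that nobody suspects could then be exposed to a new drug. The 9.4 test and stop rule would not act until someone became suspicious. Safety and tolerability are the primary objective (2.1), so a gap in a pre-exposure check deserves attention even if few women are affected.

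**Working it through.** The plan states no figure for this interval, so there is none to reproduce. The check is calendar arithmetic on the study days in 4.2.

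**Inputs**
- Last scheduled test: Day 1 (4.2, 7.8).
- Extension dispensing: Day 56 ± 2 (4.2, 6.2.5).
- End of extension: Day 336 ± 4 (4.2).
- Screening: about 4 weeks before Day 1 (6.2.1).
- Placebo arm: 10 patients of both sexes (4.1). The number of women of child-bearing potential is not given.

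**Age of the last test when extension drug is dispensed**
- Nominal: 56 − 1 = 55 days.
- Window: 54 − 1 = 53 to 58 − 1 = 57 days.
- The plan does not give the time of the first extension dose. If it is the next morning, add one day (56 nominal, at most 58).

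**The two first exposures side by side**

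| | Day 1 | Placebo women, Day 56 |
|---|---|---|
| Age of the previous test | about 4 weeks | 55 days (53–57) |
| Retest before drug | yes (6.2.2, 7.8) | none (6.2.5) |
| Contraception required | yes | yes |

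**Separate point: the extension itself**
- Day 56 to Day 336: 336 − 56 = 280 days on active drug with no scheduled test.
- Window: 332 − 58 = 274 to 340 − 54 = 286 days.

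**Scale (illustration only)**

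Expected pregnancies = annual rate × days / 365.25 × number of women. The rate of 1% per year and the numbers of women are assumptions. Section 7.8 gives a rate below 1% per year for highly effective methods.
- Placebo, Day 1 to Day 56, 3 women: 0.01 × 55 / 365.25 × 3 = 0.005.
- The same period with 10 women (the whole arm): 0.01 × 55 / 365.25 × 10 = 0.015.
- Extension, Day 56 to Day 336, 5 women: 0.01 × 280 / 365.25 × 5 = 0.04.
- The same period with 15 women: 0.01 × 280 / 365.25 × 15 = 0.11.

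These figures count all pregnancies. A scheduled test changes the course only for those that are unsuspected while drug is being given. That is a smaller number, which the documents do not allow one to estimate.

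**The case against.** The strongest objection is that the plan already accepts the same interval for women on active drug. A woman on Treatment A or B who conceives between Day 1 and Day 56 is exposed at once, with no scheduled test. A placebo woman who conceives in that period is unexposed until the extension. **This stands.** A reader might infer that placebo women carry more risk than women on active drug, and the documents do not support that. What remains is narrower: the check that precedes first exposure on Day 1 is missing at their first exposure.

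The existing controls are also real. Contraception is required throughout, patients attend every 8 weeks, and any suspicion leads to a serum test. Nothing stops an investigator from testing on slight suspicion. Section 1.2.3 reports that reproductive toxicity studies showed, in general, no adverse effects, so the documents contain no signal that calls for intensive testing. **This supports a low severity.** It does not make the controls equivalent to a test: contraception was equally required on Day 1, where the plan still retests, and 9.4 acts only on suspicion.

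One might also argue that the test frequency breaches no rule of the protocol. **That is correct.** Sections 4.2, 6.2 and 7.8 agree with one another. This is a gap in a design choice, not a contradiction.

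Finally, a reader might infer that a pregnancy unsuspected at Day 336 would escape follow-up. Section 9.4 does not say so: "All pregnancies with study drug exposure will be followed until resolution", with no time limit. Only the recall for a serum test is limited to 7 days after the last dose. The concern is late detection, not loss of follow-up by rule.

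**Conclusion.** The point holds as a low-severity patient-safety improvement. Women on placebo who enter the extension are dispensed their first SPH3127 on a pregnancy test 55 days old (53 to 57), without the pre-dose retest that the plan requires on Day 1. The calendar figures rest on the documents alone. The event figures rest on an assumed rate and assumed numbers of women, and show only that few events are expected.

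The 280 days without a scheduled test concern ongoing monitoring of all women in the extension. They are a separate, secondary matter and add no weight to the Day 56 point. Neither matter affects the statistical analysis.

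**What to change.** **Main change.** In 4.2, 6.2.5 and 7.8, add a urine pregnancy test at Day 56 for women of child-bearing potential who enter the extension. Require a negative result before extension drug is dispensed. Confirm any positive with the 9.4 serum test and hold drug until it is read. Apply the test to all arms, since testing only placebo women would reveal their original assignment.

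**Secondary change.** In 4.2, 6.2.7 and 7.8, repeat the strip at D112, D168, D224, D280 and D336. An unsuspected pregnancy would then be found earlier and, at the dispensing visits, the stop rule in 9.4 could act. The longest scheduled gap becomes 56 days (64 at most with windows), close to the main study's 55.

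**Cost.** A small amendment and no new visit. For 5 to 15 women (assumed), the Day 56 test needs 5 to 15 strips and the five later visits 25 to 75, so 30 to 90 in all if everyone stays to Day 336. Time at Day 56 is not an obstacle, because for pharmacokinetics "Sample collection will occur over 8 hours at the study site on Days 1, 28 and 56", and a strip can be read before dispensing. An occasional false positive will delay dispensing, and a strip can miss a very recent conception. Whether the urinalysis sample can be shared depends on the Study Laboratory Manual, which is not among the documents. If it cannot, a separate urine cup is needed.
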